#### 20.5 Reporting

The CI shall submit once a year throughout the clinical trial, or on request, an Annual Progress Report to the host organisation, funder (where required) and Sponsor. In addition, an End of Trial notification and final report will be submitted to the MHRA, the REC, host organisation and Sponsor.

#### 20.6 Transparency in Research

Prior to the recruitment of the first participant, the trial will have been registered on a publicly accessible database. Results will be uploaded to ISRCTN database within 12 months of the end of trial declaration by the CI or their delegate. Where the trial has been registered on multiple public platforms, the trial information will be kept up to date during the trial, and the CI or their delegate will upload results to all those public registries within 12 months of the end of the trial declaration.

#### 20.7 Participant Confidentiality

The study will comply with the General Data Protection Regulation (GDPR) and Data Protection Act 2018, which require data to be de-identified as soon as it is practical to do so. The processing of personal data of participants will be minimised by making use of a unique participant study number (uMed ID) only on all study documents and any electronic database(s), with the exception of informed consent forms, participant ID log and electronic diaries. All documents will be stored securely and only accessible by study staff and authorised personnel. The study staff will safeguard the privacy of participants' personal data. A separate confidential file containing identifiable information will be

stored in a secured location in accordance with the current data protection legislation. Photographs of vaccination sites if required (with the participants' written, informed consent), will not include the participants' face and will be identified by the date, trial code and subject's unique identifier. Once developed, photographs will be stored as confidential records, as above. This material may be shown to other professional staff, used for educational purposes, or included in a scientific publication.

#### 21 Finance And Insurance

#### 21.1 Funding

The study is funded by National Institute Health Research (NIHR), supported by the Vaccine Task Force and DHSC.

#### 21.2 Insurance

The Sponsor has a specialist insurance policy in place which would operate in the event of any participant suffering harm as a result of their involvement in the research. NHS indemnity operates in respect of the clinical treatment that is provided.

#### 21.3 Contractual arrangements

Appropriate contractual arrangements will be put in place with all third parties.

## 22 Publication Policy

The Investigators will be involved in reviewing drafts of the manuscripts, abstracts, press releases and any other publications arising from the study. Data from the study may also be used as part of a thesis for a PhD or MD.

# 23 Development of a New Product/Process Or The Generation Of Intellectual Property

Ownership of IP generated by employees of the Trust vests in the Trust. The Trust will ensure appropriate arrangements are in place as regards any new IP arising from the trial.

## 24 Archiving

Study data may be stored electronically on a secure server, and paper notes will be kept in a key-locked filing cabinet at the site. All essential documents will be retained for a minimum of 25 years after the study has finished with 5 yearly reviews. The need to store study data for longer in relation

to licensing of the vaccine will be subject to ongoing review. For effective vaccines that may be licensed, we may store research data securely at the site at least 25 years after the end of the study, subject to adjustments in clinical trials regulations. Where relevant participants' bank details will be stored for 7 years in line with the site financial policy. De-identified research data maybe be stored indefinitely, but with 5 yearly review.

General archiving procedures will be conducted in compliance to SOP R&D/Gen/Admin/022 SOP for the Archiving of Clinical Trial Data.

## 25 Sub-study – Pending Funding and Amendment

This section outlines plans for a future amendment for a sub-study if funding can be secured.

This sub-study will take place at hospital sites only.

#### 25.1 Sub-study Summary

The sub-study involves additional activity for a small subset of children enrolled in the main trial across three hospital sites. Approximately 30 to 40 children who enrol will have additional investigations performed at the visit immediately before receiving their nasal influenza vaccine, and at the visit four weeks after this. These investigations will involve insertion of a SAM-Strip to investigate mucosal immunity, and venesection for blood to investigate humoral (and where-possible, T-cell mediated) immunity.

Parents/legal guardians will remain blinded to which visit their child will receive the vaccine or placebo and will not be informed of how the timing of the investigations relate to their randomised allocation.

There will be one additional in-person visit for participants who are randomised to the late vaccine group, as they will need to attend their final follow up visit to have investigations performed four weeks after receiving their nasal influenza vaccine.

All other study activities will be performed according to the main protocol.

#### 25.2 Objectives and outcome measures

Objectives	Outcome Measures	Timepoint(s)			
	Primary				
To determine the mucosal and humoral immunogenicity of Fluenz in children aged 12 – 23 months	Mucosal and plasma influenza antibodies	Day 0 and 28 following vaccination			
Key secondary					
To assess cellular immunogenicity of Fluenz in children aged 12 – 23 months	T cell responses to influenza	Day 0 and 28 following vaccination			

#### 25.3 Study Design

#### 25.3.1 Trial design

Participants will be randomised as per the main protocol. Additional blood tests and mucosal immunity samples (via SAM-Strips) will be performed in both groups.

#### 25.3.2 Population

The sub-study population will be drawn from the main study population within participating hospital sites. The same inclusion and exclusion criteria will apply.

#### 25.3.3 Setting

Three NHS hospital sites located in Southampton, St George's hospital and Bristol.

#### 25.3.4 Study groups

The study will consist of 2 groups of children who have been randomised to either the early vaccine (EV) or late vaccine (LV) arms of the trial, as per the main protocol.

#### 25.3.5 Interventions

Additional samples will be collected from both groups. These will consist of blood tests and SAM-strips collected on both the day of vaccination immediately prior to receiving the nasal influenza vaccine, and at the subsequent visit four weeks post vaccination.

## 25.4 Sub-study Schedule of Visitations

	Early Vaco	ine Group		
	D0	D28 (-3/+7)	D56 (+7)	
In person visit	Х	Х		
Telephone contact			X	
Consent	Х	Х		
Randomisation	Х			
Vaccination with LAIV	Х			
Placebo nasal spray		Х		
Blood tests	Х	Х		
SAM-Strips	Х	Х		
Collection of SAEs, AESIs	To b	pe reported at any time up	to D56	
and MAAEs				
	Late Vacci	ine Group		
	D0	D28 (-3/+7)	D56 (+7)	
In person visit	Х	Х	Х	
Telephone contact				
Consent	Х	Х		
Randomisation	Х			
Vaccination with LAIV		Х		
Placebo nasal spray	Х			
Blood tests		Х	Х	
SAM-Strips		Х	Х	
Collection of SAEs, AESIs and MAAEs	To be reported at any time up to D56			

## 27 Appendix A

## 27.1 Schedule of visits for the Early Vaccine (EV) cohort

Early Vaccine Group					
	D0	D28 (-3/+7)	D56 (+7)		
In person visit	X	X			
Digital Questionnaire			X		
Consent	X	X			
Collection of demographic data	Х				
Medical History	Х				
Concomitant medications	Х	X	Х		
Weight	Х				
Randomisation	Х				
Vaccination with LAIV	Х				
Placebo nasal spray		X			
e-Diary information provided	X				
Study card provided	Х				
Diary Review		X			
Collection of SAEs and MAAEs	To be reported at any time up to D56				

## 27.2 Schedule of visits for the Late Vaccine (LV) cohort

Late Vaccine Group					
	D0	D28 (-3/+7)	D56 (+7)		
In person visit	X	х			
Digital Questionnaire			Х		
Consent	Х	х			
Collection of demographic data					
Medical History	X				
Concomitant medications	X	х	Х		
Weight	Х				
Randomisation	X				
Vaccination		х			
Placebo nasal spray	Х				
e-Diary information provided		x			
Study card provided	Х				
Diary Review			X		
Collection of SAEs, AESIs and MAAEs	To be reported at any time up to D56				

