## 9.1 Outcome ascertainment

Outcomes will be collected from routine GP medical records by the digital CRO, uMed. For medically attended wheeze, specific codes referring to a diagnosis of "Viral induced wheeze" and "Asthma" will be used, alongside findings of "Wheeze", and any new prescription for either Salbutamol or Ipratropium Bromide:

- 276191000000107 | Viral wheeze (disorder)
- 195967001 | Asthma (disorder)
- 56018004 | Wheezing (finding)
- 24612001 | Wheeze rhonchi (finding)
- 372897005 | Salbutamol (substance)
- 372518007 | Ipratropium (substance)

Whilst using codes of a finding of "wheeze" are most specific to the primary outcome, these codes are rarely used in practice and yield insufficient events. GP EPR data from a 3 month period indicates that, "Viral induced wheeze", and "Asthma" are the codes most commonly associated with wheezing. This

yields a population incidence of roughly 2% during a three-month period, in line with the power calculations for the study.

The primary outcome includes all events coded with a finding of "wheeze" together with the addition codes asthma/viral wheeze/salbutamol/ipratropium.

Additional medical attendances at locations other than the child's primary GP practice (e.g., hospital or other GP locations) will be determined using electronic diaries and solicited at follow up visits.

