## 12.5 Visits

The study visits and procedures will be undertaken by one of the clinical trials team. The procedures to be included in each visit are documented in the schedule of attendances (see Appendix A). Each visit is assigned a time-point and a window period, within which the visit will be conducted. If a participant cannot attend a visit, where possible, this will be re-arranged to an in-person visit within the time window. The final visit will be conducted via a digital questionnaire administered by uMed. If the questionnaire has not been completed following additional prompts by the uMed nursing delegate, then the local study team will be contacted to attempt reach out to the participant's family.

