#### 12.5.2 Diary reports

Participants' parents/legal guardians will receive a digital diary request at 7 and 14 days after each inperson study visit during the trial, issued via uMed. This will ask them whether their child has attended a healthcare provider since their last visit or diary entry. If they answer yes, they will be directed to further questions regarding the location and nature of this contact with a healthcare provider.

Participants will not be provided with a 24-hour telephone number to contact the study team for medical advice, as this would significantly impact the primary outcome measure which is dependent on the participant's family conducting their normal healthcare seeking behaviour. Participants will be advised to seek their normal routes of healthcare advice via NHS provision of they have any medical concerns regarding their child, whether or not they are considered related to the study. This information will be captured via the digital diary.

Participants will be provided with a 24h telephone number and email address to report hospital admissions to the study.

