## 12.5.4 Subsequent visits

Follow-up visits will take place as per the schedule of attendances described in Appendix A. Participants will be assessed for medical attendances, interim history and review of diary cards at these time points as detailed in the schedule of attendances.

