## 14.6 Procedures for Reporting Adverse Events

## 14.6.1 Medically attended AEs

A medically attended AE, is defined as any adverse event for which the participants' parents/legal guardians seeks medical attention for them either at hospital or from primary care. Participants' parents/legal guardians will be asked to record any medically attended AEs on their electronic diary. Medically attended AEs occurring up to 56 days post randomisation, will be directly solicited and reviewed at each study visit.

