#### 16.2 Data Recording

uMed securely collects clinical, patient-reported, and study data in compliance with GCP and regulatory standards. Data is obtained from the following primary sources:

- EHR Data: Extracted from UK general practices (EMIS and TPP systems)
- ePRO/eDiary/eConsent Data: Captured directly from patients via digital surveys for informed consent, subjective outcomes and other patient reported data as required by the Protocol
- Other Study Data: Collected from sites through digital Case Report Forms (CRFs) for protocolspecific activities

All data is stored and managed within uMed's secure cloud infrastructure on Amazon Web Services (AWS) in the London region (UK). Patient-identifiable data remains within this controlled environment. Data management includes strict governance, access control, audit logging, and filtering for National Data Opt-Out and exclusion criteria. Source data files are retained in their original form for traceability and auditability. Data handling adheres to GDPR and relevant local regulations, with access restricted to authorized personnel.

All participant reported adverse event data will be entered onto electronic diary cards (e-diaries) for a maximum of 28 days following administration of the IMP. The eDiary provides a full audit trial of edits and will be reviewed at time-points as indicated in the schedule of events. Any adverse event continuing beyond the period of the diary will be copied into the eCRF as required for safety review.

The participants will be identified by a unique trial specific number and code in any database. The name and any other identifying detail will NOT be included in any trial data electronic file, with the exception of the electronic diaries, for which consent will be obtained to store the participant email

address for quality control purposes. Only site research staff, sponsor staff, monitors (as delegated by sponsor) and University of Oxford data managers have access to view the email address.

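### Appendix A marks e-diary information and diary review only around the LAIV dose in both arms; this contradicts section 12.5.2 and, if followed, could tilt wheeze ascertainment towards the vaccine

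*Protocol*

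**What the plan says.** **Schedules (Protocol 27.1 and 27.2).** Each table has a row "e-Diary information provided" and a row for diary review. In the early vaccine (EV) arm, which gets LAIV at D0, information is marked at D0 and review at D28. In the late vaccine (LV) arm, which gets LAIV at D28, information is marked at D28 and review at D56. The study card is marked at D0 in both arms.

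**Diary requests (12.5.2).** Parents "will receive a digital diary request at 7 and 14 days after each inperson study visit during the trial". No distinction by arm or product is made.

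**Which text governs.** Section 12.5 says "The procedures to be included in each visit are documented in the schedule of attendances (see Appendix A". Section 12.5.4 provides for "review of diary cards at these time points as detailed in the schedule of attendances". Section 16.2 likewise has the eDiary reviewed at the time-points in the schedule, and has diary data entered "for a maximum of 28 days following administration of the IMP".

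**Use of the diary.** Section 9.1 states "Outcomes will be collected from routine GP medical records by the digital CRO, uMed". Attendances elsewhere, such as at hospital or another practice, "will be determined using electronic diaries and solicited at follow up visits". Section 14.11 ties the second DSMB review to 500 participants having completed their day 14 diary.

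**Other ascertainment.** Under 14.6.1, medically attended adverse events up to day 56 "will be directly solicited and reviewed at each study visit".

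**The concern.** The primary comparison is wheeze in the 28 days after LAIV against the 28 days after placebo, with every child contributing to both. A cross-over removes differences between children and, with balanced sequences, differences between periods. It does not remove a difference in how hard events are looked for if that difference travels with the product. The Appendix A marks do travel with the product in both sequences.

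The direction matters. The trial exists because an earlier phase 3 trial suggested more wheeze after LAIV in this age group (section 6). Better detection after LAIV would push the ratio towards that same signal. The DSMB review at 500 participants is exposed too: at day 14 these children are in their first period, so it compares EV with LV, and under Appendix A the LV families would have had no e-diary information.

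Parents are meant to be blind (12.4), and the outcome depends on normal care-seeking (12.5.2). A procedure whose timing depends on allocation is a possible cue.

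**Working it through.** **1. The tables against section 12.5.2.**

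| Item | EV: after LAIV | EV: after placebo | LV: after placebo | LV: after LAIV |
|---|---|---|---|---|
| Diary information (App. A) | D0 | none | none | D28 |
| Diary review (App. A) | D28 | none | none | D56 |
| Requests (12.5.2) | days 7, 14 | days 7, 14 | days 7, 14 | days 7, 14 |

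Information and review are marked after LAIV in 2 of 2 arms and after placebo in 0 of 2. Requests are symmetric. Both diary rows shift by one visit between arms, in step with LAIV, while the study card does not move, so marks lost in text extraction are an unlikely explanation.

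**2. What remains if 12.5.2 governs requests.** Section 12.5 covers procedures at visits, so it does not override requests sent between visits. Two gaps remain. Review stays LAIV-only, because 12.5.4 and 16.2 refer it to the schedule. LV families would also get their placebo-period requests before any e-diary information. Section 16.2's reference to the IMP does not settle the matter: the synopsis lists saline among the IMPs, while the holding rule in 14.12 uses the term for the vaccine.

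**3. Illustrative size.** The protocol gives no figure for the share of events outside the child's own practice or for how completely they are found. Assume a share h of 10% to 30%, of which c1 = 90% is captured after LAIV and c0 = 30% to 60% after placebo. With a true ratio of 1:

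observed RR = (1 − h + h·c1) / (1 − h + h·c0)

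| h | c0 | Observed RR |
|---|---|---|
| 10% | 60% | 0.99/0.96 = 1.03 |
| 10% | 30% | 0.99/0.93 = 1.06 |
| 30% | 60% | 0.97/0.88 = 1.10 |
| 30% | 30% | 0.97/0.79 = 1.23 |

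If c0 = c1, the ratio is exactly 1.

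In events: 2800 × 0.9% = 25.2 per product if LAIV is harmless. The first row loses 25.2 × 0.03 = 0.8 more events after placebo than after LAIV; the last loses 25.2 × 0.18 = 4.5 more.

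**4. Effect on the test.** The 2800 in section 15.1 reproduces. For 0.9% against 1.8%, 80% power and two-sided 0.05:

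n = [1.960·√(2 × 0.0135 × 0.9865) + 0.842·√(0.009 × 0.991 + 0.018 × 0.982)]² / 0.009² = 2580

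With continuity correction, (n/4)·[1 + √(1 + 4/(n × 0.009))]² = 2798 per product. Each child supplies both, so this is about 2800 children.

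Now take a simpler model: full capture after LAIV and a share s of outside events captured after placebo, so observed RR = 1/(1 − h + h·s). Using a pooled z-test with 2800 periods per product and ignoring within-child correlation, the chance of a false significant excess after LAIV (nominal 2.5%) is:

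| h | s | Observed RR | Chance |
|---|---|---|---|
| 10% | 80% | 1.02 | 2.9% |
| 10% | 50% | 1.05 | 3.8% |
| 30% | 80% | 1.06 | 4.1% |
| 30% | 50% | 1.18 | 8.0% |

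**The case against.** The strongest reply is that this is a drafting slip, not a plan for unequal ascertainment. Section 12.5.2 is explicit that requests follow both in-person visits in both arms. The Appendix A row concerns information handed out at a visit, not the issue of diaries, and giving it once at D0, as in EV, is sensible. The anomalies then reduce to one misplaced information mark in LV and one missing review mark in each arm. The LV table has another slip: it lists AESIs although section 14.8.2 says there are none. GP extraction, solicitation at each visit and the 24-hour line for reporting hospital admissions apply whatever the product.

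Most of this stands, and it rules out a stronger reading. A reader might infer from the tables that no diary exists in the placebo period, so that every child has one diary period and one without. Section 12.5.2 contradicts that. A reader might also take the extreme case in which no outside event is found after placebo; 9.1 and 14.6.1 exclude it, because such attendances are also solicited directly.

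The reply does not remove the contradiction. On paper, review of a named primary-outcome source follows the vaccine only, and the sections on review point to the faulty tables.

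**Conclusion.** The point holds as an internal contradiction with a conditional risk of bias. What is established is that Appendix A and section 12.5.2 disagree, that diary review as written is tied to LAIV in both arms, and that LV families would get placebo-period requests before any e-diary information. If sites or the platform follow Appendix A, the relative risk could be biased upward, and the cross-over would not correct it. The size cannot be derived from the protocol; 1.03 to 1.23 is illustrative and rests wholly on the assumed shares in the working.

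It might also be inferred that parental blinding is broken. The protocol does not support that. Receiving diary instructions at D0 is unremarkable in itself, and a parent would need to know, or compare with another family, that the timing differs by arm. It is a possible cue and no more.

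The matter is still more than clerical, since events not sought after placebo may not be recoverable at analysis.

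**What to change.** Make the diary rows of 27.1 and 27.2 identical: e-diary information at D0, and diary review at both D28 and D56, in both arms. Keep the requests at 7 and 14 days after both in-person visits as section 12.5.2 has them. Confirm that the uMed prompts and review tasks are configured without reference to allocation.

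The cost is two table corrections and one configuration check. No visits or participants are added, and the sample size and analysis are unchanged.

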# 28 Appendix B: Amendment History

Amen dment No.	Protocol Version No.	Date issued	Author(s) of changes	Details of Changes made
1	1.1	14th Aug 2025	[name]	
 
Clarified global end of trial defined as LVLS (section 7).
 
Amended exclusion criteria to include receipt of salicylate therapy, and receipt of an IMP within 12 weeks or five half-lives of the IMP (whichever is longer) prior to the first study dose (section 11.3).
 
The ability for investigators to immediately unblind a participant, where considered necessary, has been clarified (section 12.4).
 
Introduction of a DSMB review at 7 days post 100 participants vaccinated and 14 days post 500 participants vaccinated (section 14.11)
 
Introduction of holding rules for baseline hospitalization rate >2.5% and significant increased hospitalizations in vaccination group (p<0.05), OR a fatal/life threatening SAE considered associated with the IMP (section 14.12)
 
Clarified that in the event the study is paused for safety concerns, that a substantial amendment would be required prior to restarting (section 14.12).
 
Recommended site visit for safety assessment where clinically indicated for review of medically attended adverse events thought possibly related to the IMP (section 14.5).
 

		•	Amend references to placebo to clarify this
			is routine NHS stock normal saline stored at
			study sites.
